The abscess cavity of both groups will be gently packed with  $\frac{1}{4}$  inch plain gauze strips and the wound will be covered with 4x4 gauze and secured with tape. Patients will be instructed to leave the wound packing in place and change the outer dressing once a day until they return at 48-72 hours for their first wound recheck.

Several studies have shown that there is no clinical benefit to antibiotics in the routine management of uncomplicated abscesses. Patients with uncomplicated abscesses (defined as palpable abscess < 5 cm in a healthy patient with no history of diabetes, HIV, IVDA or immunocompromised state who has no systemic signs of infection) will not be treated with antibiotics. Patients who do not meet these criteria will be treated with antibiotics at the discretion of the provider.

A study investigator will evaluate the patient in the emergency department or clinic within 48- 72 hours for the initial follow up visit and the packing will be removed. Patients randomized to Provodine will have the contents of the foil packet reapplied to the walls of the abscess cavity and surrounding skin. Data that will be collected on initial recheck include presence or absence of fever, purulent drainage, erythema, and pain, as well as presence of new skin lesions. A new lesion is defined as a new abscess, pustule, carbuncle, or furuncle at least 5 cm away from the initial wound. Lesions within 5 cm of initial wound will be considered failures of the initial abscess treatment.

Study investigators will also record compliance with intervention and side effects. Compliance will be assessed by measuring the amount of opened foil packets and by patient report. The cure rate, as measured by the absence of fever, pain, erythema and purulent discharge, will be recorded as well as the overall assessment by the provider if wound is improving, unchanged, or clinically worsened.

Wound management will be left up to the discretion of the treating provider, but further incision and drainage, wound repacking and antibiotic use will be reserved for patients determined to be not clinically improving or getting worse and will be considered a treatment failure. Outcomes including clinical cure, rate of new lesion development in patients and HCs, and therapeutic changes to clinical management will be recorded.

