Study investigators will also record compliance with intervention and side effects. Compliance will be assessed by measuring the amount of opened foil packets and by patient report. The cure rate, as measured by the absence of fever, pain, erythema and purulent discharge, will be recorded. Wound management will again be left up to the discretion of the treating provider, but further incision and drainage, wound repacking and antibiotic use will be encouraged only for patients determined to be not clinically improving or getting worse and will again be considered a treatment failure. Outcomes including clinical cure, reinfection, rate of new lesion development, and therapeutic changes to clinical management will be recorded.

Patients will be called at home at 30 days to assess for treatment failures requiring additional intervention and new lesion development in patients and their HCs.

The figure below depicts the timing of assessments for patients (Pts) and household contacts (HCs). Outcomes include rate of clinical cure rate of initial abscess and rate of new lesion development. Therapeutic changes (e.g., addition of new antibiotics or additional incision and drainage), or unplanned health care encounters for the skin infection (e.g., urgent care visits, emergent care visits, or hospital admissions) will be considered treatment failures. Fisher's exact test will be used to compare outcomes between groups.

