## **Statistical Methods**

Continuously distributed outcomes will be summarized with the sample size, mean, standard deviation, median, minimum and maximum, and categorical outcomes will be summarized with frequencies and percentages. The number screened, the number of screen failures by reason, and the number randomized, and the number lost to follow-up by reason and the number completing the study by treatment group will be tabulated. Treatment groups will be contrasted with regard to cure (yes, no), new lesions (yes, no), and infections (yes, no) with Fisher's Exact tests. Adverse events, if any, will be listed by treatment group and case number and indicators of seriousness (serious, not serious), severity (mild, moderate, severe), and relation to the treatment (related to the treatment, unknown but not related to the treatment). All statistical testing will be two-sided with a significance level of 5%. The sample size was not derived from a statistical power calculation but was motivated by the pilot nature of this study. SAS Version 9.4 for Windows or R will be used throughout.

---

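### The rechecks collect 'side effects' but the analysis lists 'adverse events'; nothing requires collection regardless of attribution or links failure admissions to the seriousness field, so ascertainment may differ by arm

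*Combined protocol and SAP*

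**What the plan says.** **Collection.** In the Methods, the text for the first recheck (48-72 hours) and the second (7-10 days) carries the same sentence: "Study investigators will also record compliance with intervention and side effects". The sentence after it explains how compliance is measured. No sentence explains what a side effect is or how it is asked about.

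**Clinical signs.** The rechecks also collect clinical findings: "Data that will be collected on initial recheck include presence or absence of fever, purulent drainage, erythema, and pain", together with new skin lesions. The second recheck repeats these items. No arm restriction is stated.

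**Admissions.** The outcomes paragraph of the Methods counts therapeutic changes and unplanned encounters for the skin infection as failures: "urgent care visits, emergent care visits, or hospital admissions) will be considered treatment failures".

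**The 30-day contact.** "Patients will be called at home at 30 days to assess for treatment failures requiring additional intervention and new lesion development". The sentence covers patients and their household contacts and names no safety item.

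**Analysis.** Statistical Methods states: "Adverse events, if any, will be listed by treatment group and case number and indicators of seriousness", followed by severity and "relation to the treatment (related to the treatment, unknown but not related to the treatment". No count, percentage or interval for patients with events is specified.

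**The concern.** In ordinary use, a side effect is something already thought to come from a treatment, whereas an adverse event is any untoward occurrence whatever its cause. A listing that grades relation and allows for unrelated events needs the broader kind of collection. If staff take the recheck wording literally, attribution is partly decided before the relation field is filled in.

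The trial is open-label, so patient and investigator both know the arm when the question is put. In the Provodine arm the product goes onto the hands, into the abscess cavity and onto the surrounding skin. In the control arm there is no study product to which a side effect could naturally be ascribed. The word therefore invites fuller reporting in one arm than in the other.

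Admissions raise a second question. An admission for the skin infection is plainly relevant to a seriousness column, but the plan mentions it only as a treatment failure. What is at stake is whether the safety listing can be read as a comparison between arms, and whether this pilot gives the planned follow-on trial usable tolerability data.

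**Working it through.** There is no figure in the plan to reproduce and no formula to apply. The check sets the collection text of the Methods beside the analysis text of Statistical Methods.

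1. **Term collected against term analysed.** The rechecks name side effects; the analysis names adverse events. Neither is defined, and no sentence says how one becomes the other. The mismatch is confirmed.

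2. **Is collection restricted by arm?** No. The recording sentence sits within visit descriptions that cover all patients, and the listing is by treatment group. The sentence pairs side effects with compliance with the intervention, and compliance is checked partly by opened foil packets, which only the Provodine arm has. That pairing may steer staff towards the product, but it is not a restriction.

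3. **Is collection required regardless of attribution?** The relation scale includes a not-related category, so the analysis expects such events. No instruction at either recheck asks for them. The analysis presupposes a collection rule that the Methods do not contain.

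4. **What do the routine clinical items cover?** Fever, purulent drainage, erythema, pain and new lesions are recorded in everyone, so common local complaints are seen in both arms. They are recorded as presence or absence and feed cure and new-lesion outcomes; no seriousness, severity or relation is attached. Events outside that set depend on the side-effects item. Irritated hands are an example: Provodine patients apply the product to their hands and controls wash theirs with soap, yet hand skin is not among the listed items.

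5. **Admissions.** Those for the skin infection are failures. The text neither includes them in the adverse-event listing nor excludes them. Two investigators could handle the same admission differently, one listing it as serious and one not, and both would be following the protocol. An admission for another reason is not a failure under the definition, so its capture rests on how side effects is understood.

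6. **After the second recheck.** The 30-day call names failures and new lesions only. An admission between the second recheck and day 30 could therefore be learned of as a failure without any stated step that places it in the listing.

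7. **Form of the analysis.** A listing shows individual cases. The number and percentage of patients affected per arm, with an interval, is not specified.

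**The case against.** The best defence is that this is a matter of terminology. The recording sentence applies to all patients, the listing is by arm, and the relation scale shows that the authors meant to list unrelated events. The clinical signs most likely to be reported are collected in everyone. Admissions are compared as outcomes and are nowhere barred from the listing. The trial is an unpowered pilot with no safety aim, and per-arm proportions could be worked out from the listing.

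Much of this stands, and it rules out several stronger readings that a reader might infer:

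- *Control-arm or unattributed events have no way into the listing, so controls show none by construction.* The text does not say this. Recording is not restricted by arm, and a not-related category exists. For the same reason, an illustration that sets some events in the Provodine arm against zero in controls would assume the very point in dispute.
- *There is no background rate.* Pain, erythema, fever and drainage are recorded in all patients.
- *Admissions are kept out of the safety record.* The plan is silent on the overlap, and silence is not an exclusion.
- *Wide limits around zero events measure the defect.* With an assumed 65 per arm (130 enrolled, 1:1), the exact two-sided upper 95% limit for zero events is 1 - 0.025^(1/65) = 5.5%. With 50 per arm (100 completers) it is 1 - 0.025^(1/50) = 7.1%. These limits follow from sample size alone and would be the same after the fix.

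The defence does not supply the missing instruction. An intention shown by the relation scale is not a collection rule, and an event that was never asked about cannot be recovered from the listing.

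**Conclusion.** The concern holds in a limited form. The safety term collected differs from the term analysed, neither is defined, no instruction requires collection regardless of attribution, and admissions scored as failures are not tied to the seriousness field. In an open-label trial, ascertainment in the adverse-event listing may therefore differ by arm. The documents do not show that it will, or in which direction.

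The size cannot be quantified: the plan gives no expected event rate and no basis for assuming one. The conclusion rests on the ordinary meaning of 'side effects' and on the text available. The figure on assessment timing was not available, nor were any case report forms that might already ask a broader question. The cure, new-lesion and infection comparisons are not affected. This is a worthwhile, inexpensive improvement, best made before data collection because it cannot be corrected in analysis.

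**What to change.** - **Methods, both rechecks.** Replace 'side effects' with: 'any adverse event since the last contact, whether or not thought related, asked with the same question in both arms'. Judge relation to treatment afterwards, as a separate step.
- **Methods, outcomes paragraph.** State that a hospital admission counted as a treatment failure is also entered in the adverse-event listing with its seriousness.
- **Statistical Methods.** Add the number and percentage of patients with at least one event by arm, with exact 95% confidence intervals, alongside the listing.

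Two optional additions follow from the same text. The same question could be asked at the existing 30-day call, which currently names no safety item. The relation category that joins unknown with not related could be reworded so that an undetermined relation has a clear place.

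The cost is wording on the recheck form and one summary table, with no new visits or staff. The downside is slightly more recording time per contact and more minor events listed in both arms.

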**Hypothesis**

We believe patients who use Provodine as an antiseptic and hand wash once daily for at least 7 days will have better healing, better health outcomes, fewer treatment failures and fewer infections themselves and among their household contacts (HCs) than those who do not use Provodine.

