After the packing is removed, all patients will be instructed to cleanse the abscess at home by soaking in water once a day and gently patting the wound dry. Patients will follow specific instructions for wound management once a day after washing.

After cleansing and drying the abscess, the patients randomized to the Provodine arm will wash their hands with soap and water, pat dry, and apply the contents of one foil packet of Provodine to dorsum and palmar aspects of hands and fingers and rub hands and fingers together for one minute to ensure all skin distal to the wrist is covered. They will then apply the contents of a second foil packet to the walls and floor of the abscess cavity using a Q tip applicator. The patient will then apply a third foil packet of Provodine to the skin surrounding the abscess within 5 cm diameter of the wound using a separate Q tip. After applying Provodine to the abscess and surrounding skin, they will be then gently rinse their hands with water, pat hands dry, and cover the wound with a 4x4 gauze dressing.

The patient will also be instructed to keep a Ziploc bag of empty Provodine foil packets to assess compliance at follow up visits.

[figure not shown]
Patients randomized to standard care will cover wound with 4x4 gauze dressing and wash hands with soap and water for one minute. Patients will be instructed to continue to perform once daily cleansing/treatments until they are seen for their second wound recheck or until wound cavity has closed.

The patient will return for a 2nd visit between 7 and 10 days for a second wound recheck. Data that will be collected will be the same as on initial recheck including the presence or absence of fever, purulent drainage, erythema, and pain, as well as presence of new skin abscesses in the patient or HCs.

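### Side effects are recorded only at the two wound rechecks; the 30-day call does not ask about them, so adverse events after day 7-10 are not systematically collected

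*Combined protocol and SAP*

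**What the plan says.** In the Methods, the text for each of the two wound rechecks carries the same sentence: "Study investigators will also record compliance with intervention and side effects". The first recheck is when "they return at 48-72 hours for their first wound recheck"; the second falls "between 7 and 10 days for a second wound recheck". The last planned contact is by telephone, when patients are "called at home at 30 days to assess for treatment failures requiring additional intervention and new lesion development in patients and their HCs". The failure definition in the same section goes beyond added treatment: "unplanned health care encounters for the skin infection (e.g., urgent care visits, emergent care visits, or hospital admissions) will be considered treatment failures".

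Home application of Provodine begins once the packing has been removed at the first recheck. Once-daily home care then runs "until they are seen for their second wound recheck or until wound cavity has closed". The Hypothesis describes use "as an antiseptic and hand wash once daily for at least 7 days", with no upper limit.

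Under Statistical Methods, "Adverse events, if any, will be listed by treatment group and case number and indicators of seriousness", followed by severity and relation to treatment. No collection period or method of ascertainment is given. Timeline and Estimated Costs plans to enrol until 100 patients have completed the second follow-up and expects about 130 enrolled.

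**The concern.** The efficacy aims for new lesions and for household infections run to 30 days, but the planned questioning about side effects stops at the second recheck. The call's purpose is stated, and safety is not part of it. A reaction that starts, or is first noticed, after day 7-10 therefore has no planned route into the adverse event listing.

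Because the listing has no window, its reader cannot tell whether a patient without an entry had no event or was not asked. This matters in a pilot whose results are meant to inform a larger trial (Study Design). It matters most for patients who miss the second recheck, because the plan never asks them about the period in which they applied the product themselves.

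**Working it through.** The documents give no figure of their own to reproduce. The check is a comparison of contacts followed by day counts.

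**Side-effect collection by contact (Methods)**

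| Contact | Timing | Side effects named? |
|---|---|---|
| First recheck | day 2-3 (48-72 hours) | Yes |
| Second recheck | day 7-10 | Yes |
| Telephone call | day 30 | No; failures and new lesions only |

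**Follow-up without a planned side-effect question**

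- Second recheck on day 10: 30 − 10 = 20 days; 20/30 = 67%.
- Second recheck on day 7: 30 − 7 = 23 days; 23/30 = 77%.

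**Patients with no side-effect question after home use begins**

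- Inputs from Timeline and Estimated Costs: about 130 enrolled, 100 completing the second recheck.
- 130 − 100 = 30; 30/130 = 23%.
- The last possible side-effect record for these patients is at 48-72 hours, before any home use. This does not depend on when use is meant to end.
- The allocation ratio is not stated. Assuming equal allocation and equal attrition, about 15 of the 30 would be in the Provodine arm; without those assumptions the number could lie anywhere from 0 to 30.

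**Can home use pass the second recheck?**

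- Between the rechecks, home use spans 7 − 3 = 4 days at the shortest and 10 − 2 = 8 days at the longest.
- If the Hypothesis means seven daily home uses, and the first is on the day the packing is removed, they occupy days 2-8 or days 3-9. That is 1 to 2 days beyond a day-7 recheck and complete by a day-10 recheck.
- If the 7 days are counted from the first clinic application on day 0, they can be reached by a day-7 recheck.
- The stopping rule in the Methods joins the recheck and wound closure with *or*, without saying whether the earlier or the later applies.

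Use after the second recheck is therefore possible under some readings of the text, but the text does not instruct it.

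**The case against.** The strongest reply is that the two collection points span the treatment period. On the ordinary reading of the stopping rule, home use ends at the recheck or at closure, whichever comes first. The remaining 20 to 23 days are then off treatment, and a share of calendar time is not a share of risk. This stands as a limit on the percentages. It does not answer the case of a delayed reaction, or of the patients who miss the second recheck.

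A reader might go further and infer three things that the documents do not support:

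- **That events from continued use are lost.** This treats use beyond the second recheck as established. It is one reading of an ambiguous sentence.
- **That losses fall mainly in the Provodine arm.** The argument would be that only that arm can go on using the product, so it rests on the same reading and has no other support.
- **That late admissions for the infection are missed.** Such encounters count as treatment failures, and the call is made to assess failures. The wording about additional intervention is somewhat narrower than the definition, but inferring that admissions escape is over-literal. They would be logged as failures rather than adverse events. Encounters for other reasons, such as a product reaction, are the ones with no prompt.

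It is also fair to say that spontaneous reports, including any made during the call, could enter the listing, and that Statistical Methods makes no claim of 30-day coverage. Late events are thus not systematically collected, which is different from being certain to be missed. Finally, the figure on timing of assessments and the consent pages are not available here, so whether either provides for later reporting cannot be checked.

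**Conclusion.** The point holds as a gap in collection. On the available text, nobody is asked about side effects between the second recheck and day 30, which is 20 to 23 of 30 days. About 30 of 130 patients would never be asked about home use at all. The adverse event listing does not disclose either limit.

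The count of 30 rests on the plan's own enrolment estimates and on reading the shortfall as patients who do not complete the second recheck; a few may simply still be awaiting it when the hundredth patient completes. The number of late events cannot be estimated from the documents. No conclusion about differential loss between arms, or about missed infection-related admissions, follows from the text.

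The planned comparisons are unaffected. The change is worth making because information not asked for at day 30 may not be recoverable later, and the call is already planned for every patient.

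**What to change.** In the Methods paragraph on the 30-day call, add two questions, asked in the same words in both arms:

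1. Any side effect or new medical problem since the last completed visit, with onset date.
2. Any urgent care, emergency or hospital visit for any reason, whether or not treatment was added.

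In the Provodine arm only, also ask the date of last product use; the question does not apply to the soap-and-water arm.

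In Statistical Methods, state that the adverse event listing includes these answers and that its window runs to day 30.

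Reconcile the Hypothesis with the stopping rule for home treatment in the Methods, so that it is clear whether use can continue past the second recheck. Which rule applies is for the investigators to decide.

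The cost is a slightly longer call, added lines on its form, and some extra non-serious events to list. No visit, sample size or test changes. The questions help only for patients who are reached at 30 days.
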